1.6.1 Multi-Site Study

1.0 * Is this a multi-site study:

☐ Yes ☒ No

ID: Pro00003276 View: 1.7 Section Chief and Service Line VP approvals

Please upload the approval of the Section Chief, if applicable and the Service Line VP.

1.0 * Institutional Approval Document:
[Request to Conduct Research.pdf\(0.01\)](#)

ID: Pro00003276 View: 2 Study Objectives & Design

Study Summary

1.0 Funding End Date:
3/31/2023

2.0 * Abstract. Please provide a brief description of the study.

The purpose of this study is to evaluate a new control (i.e., the vision-guided shared (VGS) control) for a wheelchair-mounted assistive robotic manipulator among powered wheelchair users. This study will consist of a questionnaire about general demographics, health information, and previous experience with assistive

technology. Several tests will also be administered to test upper extremity function and ability as well as to test spatial orientation and visualization ability. Participants will then undergo a training phase with the assistive robotic manipulator mounted on a table to assess if they will be eligible for participation in the study. Eligible participants will move on to a second training phase where they will be asked to learn and practice slightly more complex tasks while using the vision-guided shared controller. After this training the assistive robotic manipulator will be mounted to the participants wheelchair, a table, or a stand and they will be asked to complete a number of everyday tasks from a task list. At the conclusion of the study, we will conduct a brief semi-structured interview with each participant and obtain more insight on how participants perceive the ease-of-use and usefulness of the VGS control.

3.0 * Describe the study objectives. Please include primary aim and hypothesis, if applicable any secondary aims and hypotheses.

Aim: To evaluate the Vision Guided Shared (VGS) control among 21 powered wheelchair users who will use a wheelchair-mounted ARM to complete a set of functional manipulation tasks.

Hypothesis 1: Subjects will be more efficient when using the VGS control as opposed to the default control, as measured by the number of mode switching, and time taken to complete individual tasks.

Hypothesis 2: Subjects will be more effective when using the VGS control as opposed to the default control, as measured by the number of tasks successfully completed.

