*** Does clinical expertise need to be enlisted?**

☐ Yes ☒ **No**

If yes, please provide the provisions for enlisting the services of a clinician with appropriate expertise and privileges to perform duties, if the investigator is not a clinician [i.e. reviewing the data, adverse events,

and new study findings; also making required decisions to protect the health of the subject (e.g., stopping the participant's involvement in the study or determining when to notify the subject or the subject's health care provider of information that may affect the health of the subject)]]:

4.0 Please upload any surveys, questionnaires, and data collection forms.

Document	Description	Version Number
View Cube Comparison(0.01)		0.01
View Interview Quesions(0.01)		0.01
View NASA-TLX(0.01)		0.01
View Paper Folding(0.01)		0.01
View Questionnaire(0.01)		0.01
View Satisfaction(0.01)		0.01
View SUS(0.01)		0.01

ID: Pro00003276

View: 4.1 Research study methods: analysis Plan

1.0 * Please describe the analysis plan for the study (it is acceptable to refer to the sponsor/multi-site protocol for section if applicable):

Statistical analyses will be preceded by a detailed descriptive analysis of the data, using standard descriptive summaries and graphical techniques. The task completion time will be aggregated over the self selected tasks. The key variables including the aggregated task completion time, [mode switching frequency], success rate, NASA TLX score, and SUS score will be examined to ensure that proposed statistical techniques are suitable. Significance level will be determined at 0.05 for all statistical tests. We will first use scatterplots to show each participant's key variables on the two interventions. Different symbols will be used to indicate the order of intervention for each participant and the line of equality will be superimposed for ease of interpretation. We assume neither carry-over nor period effects would be a problem, thus will use a paired t-test to compare the two interventions on all key variables. Qualitative data from the semi-structured interviews will be audio recorded and transcribed, and then analyzed using the affinity diagramming technique to extract themes.

ID: Pro00003276

View: 5 Sub-Studies

1.0 * Is there a sub-study or are there sub-studies associated with this study?

There is no sub-study associated with this study.

ID: Pro00003276

View: 6 Study Population Summary

Study Population Summary

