1.0 * What is the maximum number of subjects you plan to enroll at VAPHS?

We aim to recruit a total of 21 participants.

2.0

* Do you plan on enrolling patients into different categories:

☐ Yes ☒ No

If yes, please explain:

3.0 If this is a multi-site study, indicate the projected total subject accrual:

4.0

* Please provide a justification for the sample size:

[Based on our preliminary work, in the lab testing condition, the VGS control could reduce the task completion time by an average of 30% (ranging from 0.03% for the simple door handle task to 55% for the relatively difficult knob turning task). The functional tasks in our task list will contain more complex tasks,

thus we can reasonably assume at least 20% reduction in task completion time when using the VGS control as opposed to the default control for this power analysis.] Given an alpha of 0.05, a 20% reduction in task completion time, and a 25% standard deviation in the difference between the two interventions, we will need 12 participants to obtain 80% power for the study. We will, therefore, recruit 16 participants to account for attrition for the lab testing session. For the home testing session, since this is a pilot study, there is no prior data from our group and published paper. Thus, it is not applicable to calculate a power analysis. We aim to recruit 3-5 participants to assess the feasibility and collect preliminary data. Power analysis was performed using the G*power 3.1.9.2.

ID: Pro00003276

View: 6.1 Study Population

Study Population

1.0 * Check all that apply to describe your study population:

	Study Population
	Non-Veterans
	Special Populations
	Veterans
	Vulnerable populations
	Other

2.0 * Indicate the inclusion criteria for enrollment:

The inclusion criteria are (1) 18 years of age and older; (2) using a power wheelchair as primary means of mobility; (3) having self reported difficulties in performing everyday manipulation tasks such as reaching for a glass of water, opening a refrigerator, and picking up a toothbrush.

3.0 * Indicate exclusion criteria for enrollment:

The exclusion criteria are (1) people with impaired vision; and (2) people with pressure ulcers that prevent them from sitting continuously for an extended period of time.

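### The sample-size statement and the analysis plan leave the sidedness of the test unstated: 12 participants for 80% power fits a one-sided 0.05 test, but a two-sided one has 71% power at 12 and needs 15

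*Combined protocol and SAP*

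**What the plan says.** View 6 (Study Population Summary), item 4.0, sets out the calculation. It begins "Given an alpha of 0.05, a 20% reduction in task completion time". The variability and the resulting number are then given together: "25% standard deviation in the difference between the two interventions, we will need 12 participants to obtain 80% power for the study". The effect is presented as a cautious choice ("we can reasonably assume at least 20% reduction in task completion time") against an average reduction of 30% in preliminary lab work. The next step is "We will, therefore, recruit 16 participants to account for attrition for the lab testing session". The software named is G*Power 3.1.9.2. The three to five home-testing participants are a separate pilot group with no power calculation.

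View 4.1, item 1.0, plans a paired t-test on all key variables, with no period or carry-over term, and fixes the level: "Significance level will be determined at 0.05 for all statistical tests".

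View 2 (Study Objectives & Design), item 3.0, words the hypotheses directionally, for example "Subjects will be more efficient when using the VGS control as opposed to the default control".

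None of these places says one-sided or two-sided.

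**The concern.** A paired t-test described only by its 0.05 level is ordinarily run two-sided, and it is what an analyst following View 4.1 would most likely run. The figure of 12 does not give 80% power for that test with the stated inputs, but it does for a one-sided test at the same level. The sample size may therefore have been set for a different test from the one that will be reported.

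Two things depend on this. First, the step from 12 to 16 tells the team that four lab participants can be lost without harm to the power claim. The protocol has several routes to such losses: the pretest can end participation, a participant may choose a single 3-hour visit, and anyone may withdraw or decline tasks. Second, a one-sided 0.05 test allows twice the false-positive rate in the favoured direction that a two-sided 0.05 test allows (0.05 against 0.025). That choice should not be left open until the data are seen.

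**Working it through.** **Inputs (View 6, item 4.0; test from View 4.1, item 1.0)**

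- Mean paired difference: 20%
- SD of the paired difference: 25%
- Alpha: 0.05, sidedness not given
- Target power: 80%
- Stated requirement: 12; recruited for the lab session: 16
- Test: paired t-test

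**Method**

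Standardized effect: dz = 20/25 = 0.80.

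For n completers, df = n − 1 and the noncentrality is 0.80 × √n. Power is the probability that a noncentral t variable with that df and noncentrality exceeds the critical value t(1 − 0.05; df) for a one-sided test, or falls outside ±t(1 − 0.025; df) for a two-sided test.

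**Reproducing the stated 12**

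At n = 12 the noncentrality is 0.80 × √12 = 2.771, with df = 11.

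- One-sided 0.05: critical value 1.796, power 82.9%. At n = 11 power is 79.5%, so 12 is the smallest n that reaches 80%. This matches the plan.
- Two-sided 0.05: critical value 2.201, power 71.4%. This does not match.

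**Power by number of completers, dz = 0.80**

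| Completers | Lost from 16 | One-sided 0.05 | Two-sided 0.05 |
|---|---|---|---|
| 12 | 4 | 82.9% | 71.4% |
| 13 | 3 | 85.8% | 75.4% |
| 14 | 2 | 88.2% | 79.0% |
| 15 | 1 | 90.3% | 82.1% |
| 16 | 0 | 92.0% | 84.8% |

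The smallest n for 80% power is 12 one-sided and 15 two-sided. With 12 completers and a two-sided test, the smallest reduction detectable with 80% power is 22.2% rather than 20%, with the SD held at 25%.

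**Other routes to about 12**

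- Two-sided normal approximation: n = ((1.960 + 0.842)/0.80)² = 12.26, which rounds up to 13. Approximate power at 12 is 79.1%. This ignores the t distribution on 11 degrees of freedom.
- Two-sided exact t on a log scale: |ln 0.80|/0.25 = 0.893, for which 12 gives 80.3%. The documents mention no log transform and do not describe the 25% as a log-scale SD.

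The one-sided exact t is the only one of these that uses the stated inputs as written with the named test and gives 12 as the minimum.

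**Attrition allowance**

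Going from 12 to 16 implies a loss of 1 − 12/16 = 25%; the plan states no rate. If the same proportion were applied to 15 completers, 15/0.75 = 20 would be recruited for the lab session. With three to five home participants added as a separate group, that makes 23 to 25, above the planned total of 21.

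**The case against.** The strongest reply is that nothing has been miscalculated. The figure follows exactly from the stated inputs under a one-sided test, and the directional evidence points that way: all three hypotheses predict that the new control is better, and the justification for enrolling non-Veterans (View 6.1.1, item 2.0) ties power to showing superior performance. This stands in part. A reader might infer that the plan implies a two-sided test, so that 12 is an arithmetic error and 15 the correct requirement. The documents do not support that, because they are silent on sidedness. Equally, a directional hypothesis states what is expected and does not define a one-sided rejection region, so the silence does not establish a one-sided test either.

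A reader might also infer that only a one-sided test can yield 12. That is true of the exact t-test on the untransformed scale. The normal-approximation and log-scale routes come close to 12 or reach it, although the documents describe neither. One-sided is the likeliest source, not a proven one.

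The last reply is that the consequence is a worst case. The plan recruits 16 for the lab session, both controls are compared in about two hours of testing, and 20% is described as a floor. With a 30% reduction and the same SD (dz = 30/25 = 1.20), two-sided power at 12 is 96.5%. This also stands: 71% applies only if the test is two-sided, all four spare recruits are lost and the true reduction is 20%. It does not rescue the stated claim, which is 80% power at 12 for a 20% reduction.

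**Conclusion.** The concern holds as an unstated sidedness with a material effect on the power claim, not as a proven error of arithmetic. If the paired t-test is two-sided at 0.05, the stated 12 gives 71.4% power (a miss rate of about 29% rather than 20%). Fifteen completers are then needed, and the 16 lab recruits can absorb one loss rather than four. If it is one-sided at 0.05, the stated figure is right (82.9%) and the defect is that neither section says so.

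These numbers take the plan's 20% and 25% at face value on the percentage scale, with an exact paired t-test and no counting of home participants toward the lab comparison. Even two-sided, the design keeps at least 80% power if no more than one of the 16 is lost. For that reason this should be fixed, but it does not undermine the design.

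**What to change.** State the sidedness in View 6, item 4.0, and in View 4.1, item 1.0, before any analysis.

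- **If two-sided 0.05:** replace the requirement of 12 with 15 evaluable lab participants. Report power of 85% with 16 completers, 82% with 15 and 71% with 12, and drop the claim of 80% power at 12. Recruitment can stay at 16, provided the text says that the margin is one participant. Recruiting 20 to keep the implied 25% allowance is an option, not a necessity, and the planned total would have to rise to hold it alongside the home group.
- **If one-sided 0.05:** keep 12 and say explicitly in both places that the test is one-sided at 0.05 and in which direction.

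The cost is one reworded paragraph in the sample-size section and a matching phrase in the analysis plan, with no extra participants. Under the two-sided choice the stated power becomes less favourable. Under the one-sided choice the plan openly accepts a 0.05 error rate in the favoured direction.

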*** Describe why you cannot complete enrollment in this study without the use of Non-Veterans:**

1. Specify why you require Non-Veterans in your study. Include information in your justification related to your study aims/goals; What role will the Non-Veteran population have in the study?

Given the nature of this research, which focuses on individuals who have limitations with activities of daily living, who use an electric powered wheelchair as primary source of mobility, our recruitment pool is small. There are insufficient Veterans available to complete this study in accordance with 38 CR 17.45 and 38 CFR 17.92. This necessitates recruiting both veterans and non-veterans for our research.

2. Provide information as to why there are insufficient Veterans suitable for this study. Include proof, whether through statistics, or another method, that you have used your resources in a good faith effort to enroll Veterans; Example- 'We are studying a rare disease that affects a very small population, in which Veterans would be an even smaller portion of that population.' *Provide the appropriate diagnostic statistics to support this*

We will need to recruit $n=21$ subjects to have sufficient power to obtain statistically significant data as to the superior performance of our custom vision-based control. We have only 19 Veteran participants in the HERL research registry that live within Pennsylvania and use a power wheelchair for the majority of their mobility. Of these registry participants, not all live close enough to Pittsburgh to participate, meet the inclusion/exclusion criteria or will want to participate in this study. Also, the information obtained from this study could be generalized to benefit the well-being of all power wheelchair users, including veterans. According to VHA Directive 1200.01 non-veterans may be recruited when there are insufficient veterans suitable for the study. According to the HERL research registry, we find this to be the case. We, therefore, would need to enroll non-Veterans to get statistical power for the study. However, we will also make every effort to actively recruit veterans into this study.

3. Provide information about how the inclusion of the Non-Veteran population will fulfill/remains consistent with the VA Mission. Explain how including Non-Veterans will enhance your study, yet still pertain to the Veteran population.

VA's Mission is to fulfill President Lincoln's promise: "To care for him who shall have borne the battle, and for his widow, and his orphan" by serving and honoring the men and women who are America's Veterans.

We believe the study results will provide knowledge base to help expand the manipulation capability of veterans with disabilities who use electric powered wheelchairs and improve their independence with activities of daily living.

4. How will the inclusion/recruitment of Non-Veterans benefit Veterans and their well-being?

It is necessary for us to include the veterans and non-veterans to increase the sample size and generalize the results to people who use electric powered wheelchairs as a primary source of mobility. We will meet the aims of the study, by enrolling veterans and non-veteran wheelchair users and having them test the our custom vision-based control for the assistive robotic manipulator.

Please upload the Inclusion of Non-Veterans Worksheet here:

- 3.0 * If your study is a clinical trial, please indicate where the VHA Notice of Privacy Practices (VA Form 10-0483) will be stored once signed:**
Not applicable.

ID: Pro00003276

View: 7 Risk/Benefit Assessment-Risks

Risk/Benefit Assessment-Risks

- 1.0 * Risk classification for this study (select one).**

Name
 Minimal Risk
 Greater than Minimal Risk

- 2.0 * Basis for making the above recommendation:**

1. Participants will evaluate a new control approach for an off-the-shelf wheelchair-mounted robotic arm for a series of everyday functional tasks, and thus will not be exposed to greater risks than what they experience in everyday life.
2. There is a risk of breach of confidentiality.

- 3.0 * Describe the safety precautions that will be taken to minimize risks/harms:**

There is the risk that the device/control could malfunction. To minimize this risk, the investigators will be working in close proximity to the subjects and provide supervision as needed. The device is designed to operate under slow speeds and allows investigators to specify safety zones where the arm cannot reach. In addition, safety switches are installed and investigators have the ability to completely shut down the operation of the device for any reason. Thus, no physical injury (e.g., swinging around and hitting the subject) can occur using this device.

Participants may experience frustration while learning to use a new device. Subjects will be provided with extensive training and also be informed that they may take a break and/or discontinue the study at any time. Subjects will also have the option to decline to complete a task if they are unable or choose not to.

In the home testing scenario, there are risks of damage to the testing objects and leaving tape trails on the object. To minimize the risk, no fragile items will be used as testing objects; also, the investigators will be working alongside the participants, giving instructions on robotic arm operation to avoid damage. In addition, no residue tape will be used for taping the fiducial tags to reduce the risk of leaving the tape marks on the object.

There is a potential risk for a breach of confidentiality from completing the questionnaires, the video recording during the testing session, and audio recording of the exit interviews. To minimize this risk, only associated research staff will have access to identifiable study information. Research activities that are video recorded will be recorded from the neck down. If someone's face is inadvertently included, investigators will blur out the subject's face prior to future use.

- 4.0 * Provide details regarding the nature of each risk using the area provided below:**

Risk Name
View Interviews
View Research activities
View Questionnaires

5.0 *** Do you plan on using the research answering service:** ☐ Yes ☒ No

If yes, please Upload the research answering service form:

6.0 **If your study involves a treatment or intervention, please upload the Patient ID Card:**

ID: Pro00003276 View: 7.1 Risk/Benefit Analysis-Potential Benefits and Alternatives

Risk/Benefit Analysis-Potential Benefits and Alternatives

Describe any potential for benefits to participants in this study:

1.0 *** Direct and Indirect Benefits to Subjects:**
There are no direct benefits to participants in this study.

The proposed work may benefit society by maximizing the potential of ARMs in assisting Veterans with everyday manipulation tasks and supporting the adoption of this advanced assistive technology. The use of enhanced ARMs in home and community could potentially lead to improved independence and the ability of Veterans with upper limb impairments to integrate into the community, as well as reduced attendant care need and cost.

2.0 *** Describe alternatives (research or non-research) that are available to subjects if they choose not to participate in this study:**
Alternative to participate is not to participate in this study. There also may be other projects the individual may qualify for.

ID: Pro00003276 View: 8 Methods of Recruitment and Retention

Recruitment Methods and Materials used for Retention

1.0 *** Select recruitment methods used on this study:**

Name
 Mail Campaign
 Referral by independent source
 Advertising such as fliers, letters, or ads (newspaper, TV, radio)
 Web Site
 Research registry
 Selected from pre-existing records
 Pre-existing relationship with participants
 Other

If Other Methods Specify:

2.0 *** Specify how subjects will be identified and how study eligibility will be determined:**
As stated on pg. 11 of the grant, subjects will be recruited through IRB approved registries developed by the Human Engineering Research Laboratories and the Department of Physical Medicine and Rehabilitation.

They also can be recruited through Pitt+Me. All registry participants have provided informed consent to be contacted for future research studies.

All registry participants have provided informed consent to be contacted for future research studies. The IRB approved flyer for this study will be provided to the registry investigators to distribute to potential subjects according to the procedures established in the registry IRB approved protocols. In response to the flyer, potential subjects will directly contact the research team if interested in participating.

We also plan to recruit through distributing the recruitment flyer to rehabilitation facilities throughout the UPMC Center for Assistive Technology (CAT) and VAPHS. Potential subjects recruited through the CAT and VAPHS wheelchair clinic will be approached by their treating provider, asked if they would like to participate and will be given a flyer. The recruitment flyer mentioned is the same as above. We also intend to utilize the VAPHS Facebook page to post a flyer. Participants may also be recruited by placing flyers at informational tables sanctioned by the VAPHS Research Office. Study team members may elect to sit at the informational tables to provide information and enroll participants.

Flyers may be posted in local rehabilitation facilities, outpatient facilities, and disability organizations. Participants may also be recruited via flyers in print media (magazines, newspapers, newsletters). The flyer may also be posted on the HERL website. The flyer instructs potential subjects to contact HERL for additional information. No recruitment materials will be used without IRB approval. Subjects who wish to participate will call the laboratories and be scheduled for testing.

Individuals who are participating in other research studies at HERL may be given the study flyer and asked if they would like more information. If yes, the individual may be introduced to a member of the research staff.

3.0

